11.4.2. Pre-Operative/Baseline Visit

The Pre-operative/Baseline Visit will occur prior to the subject having surgery. The assessments below must be completed prior to study surgery. This visit may be combined

with the Screening/Enrollment Visit and occur up to 3 months prior to surgery with confirmed absence of infection.

- Urine pregnancy test
- Medical history and physical examination: assessment of urinary tract infection (UTI) or other vaginal infection
- Pelvic examination, vaginal length measurement
- Prolapse grading (POP-Q scoring)
- Assess baseline quality of life (PFIQ-7), sexual functioning (PISQ-12), pelvic floor symptoms (PFDI-20)
- Assess baseline level of pain (TOMUS pain scale) and analgesic use
- EQ-5D for health status
- Assessment of risk factors (includes menopausal status, estrogen use, age, smoking, diabetes status, body mass index, hysterectomy status, concomitant procedures, surgeon training and expertise)

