12.3.5.2. Subjects with office-based intervention for recurrence

Adverse procedural/device event rates and QOL information will be collected for 36 months, regardless of whether or not the subject has office-based intervention for recurrence.

Event rate for each of device-related or procedure-related adverse events of specified AE type (Xenform erosion, Xenform exposure, dyspareunia) during the period after the intervention will be summarized by treatment group. Treatment groups will be compared using Cox regression for the event-free survival time (starting at the time of first office based intervention) with treatment arm.

For each QOL instrument, a comparison using t-test will be performed between native tissue repair and Xenform group on the basis of QOL score at the first scheduled follow-up after office-based intervention for recurrence.

A two sample t-test will be used to compare groups with office-based intervention for recurrence and without intervention within each treatment group. QOL score change will be reported from the last follow-up visit before office-based intervention for recurrence, to the next scheduled follow-up visit after office-based intervention for recurrence within each treatment group. For those subjects without recurrence, we will use baseline as the “before” time point in analysis, and the QOL data at 6 month follow-up visit as the “after” time point.

Similarly, event rate for each adverse device and procedure-related event type specified (mesh erosion, mesh exposure, dyspareunia), will be compared between subjects with office-based intervention for recurrence and those without. This will be done using a Cox regression of time to the first onset of each adverse event after the starting time to compare groups with office-based intervention for recurrence and within each treatment group. The starting time will be baseline for those subjects without intervention, and time of office-based intervention for recurrence for those with intervention.

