12.3.5.3. Subjects with surgical intervention for recurrence

The above mentioned analyses for the subgroup with office based intervention for recurrence will be repeated for subjects with surgical intervention for recurrence.

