12.3.5.4. Subjects with surgical intervention for recurrence or complications

Each of device-related or procedure-related adverse events during the period after the re-surgery will be summarized by the vaginal compartment(s) (i.e. apical only, anterior only, apical and anterior) treated in the index procedure within each treatment group.

12.3.6. **Additional Data Analyses**

- Assessment of EQ-5D score for health status at 12, 24 and 36 month as compared to baseline
- Assessment of SSQ-8 score for surgical satisfaction at 6, 12, 24 and 36 month

Propensity score adjusted confidence intervals described in Section 12.2.3 (Propensity Score Methodology) will be used to summarize EQ-5D and SSQ-8 score improvements between two groups.

12.3.7. **Sub-Analysis for Interventions for Complications**

The above sub-analyses in Section 12.3.5 (Sub-Analysis for Sling Repair and Interventions for Recurrence) will be repeated for re-surgery for complications or recurrence.

12.3.8. **Interim Analysis**

An interim analysis will be performed at 12 months from the last subject enrolled in the study; all subjects will be followed to 36 months for the primary endpoint and final analysis. This analysis will consist of the primary and some or all of the secondary endpoints and demographics if deemed necessary.

Descriptive statistics by treatment arm along with the 95% confidence interval for the treatment difference will be reported after adjusting for propensity scores¹. The descriptive statistics includes mean, standard deviation, n, minimum, and maximum for continuous variables and frequency statistics for discrete variables.

¹ To support United States Premarket Approval Activities, as agreed to on the Presubmission call held on May 24, 2017 (Q170382), Boston Scientific will submit descriptive statistics for the submission of the PMA, which per reclassification document number 2015-33165, is required to be accepted and filed on or before July 5, 2018.

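### The within-arm comparisons of women with and without office-based re-intervention use unlike Cox start times and unlike QOL windows, and a related model uses a covariate that overlaps the primary endpoint

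*Combined protocol and SAP*

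**What the plan says.** All references are to the combined protocol and SAP.

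- **Cox model, 12.3.5.2.** Within each arm, erosion, exposure and dyspareunia are compared between women with and without office-based intervention for recurrence, by a Cox regression "of time to the first onset of each adverse event after the starting time". The start is defined by group: "The starting time will be baseline for those subjects without intervention, and time of office-based intervention for recurrence for those with intervention". Under 11.4.2 the baseline visit may "occur up to 3 months prior to surgery with confirmed absence of infection".
- **QOL, 12.3.5.2.** A two-sample t-test is used "to compare groups with office-based intervention for recurrence and without intervention within each treatment group". For women with intervention, "QOL score change will be reported from the last follow-up visit before office-based intervention for recurrence" to the next scheduled visit after it. For the others the text reads "For those subjects without recurrence, we will use baseline as the" starting point, with month 6 as the end point. The comparison group is women without intervention in one sentence and women without recurrence in the other.
- **Repeats.** Under 12.3.5.3 these analyses "will be repeated for subjects with surgical intervention for recurrence". Under 12.3.7 they "will be repeated for re-surgery for complications or recurrence".
- **Covariate, 12.3.4.** A logistic model of the primary endpoint in each group includes office-based intervention for recurrence. Section 11.5 gives a pessary as one example of such an intervention, and defines recurrence as anatomic plus symptomatic failure. Section 7.1 names pessary use in the third component of the primary composite.

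Sections 12.3.4 to 12.3.7 mention no time-dependent covariate, landmark, matched window or caveat for these comparisons.

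**The concern.** A Cox model compares hazards at equal clock time. Under the planned rule, day 1 is the day after an office intervention, months after surgery, for one group. For the other group it falls at or before the index operation. Unless the adverse-event hazard is flat over 36 months, the hazard ratio reflects time since surgery as well as any effect of the intervention.

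The QOL comparison has the same flaw in another form. The comparator window spans the index operation, which was done to relieve a bothersome bulge that every woman had at entry (9.2). The intervention window lies wholly after that operation. Women without intervention are credited with the surgical gain and women with intervention are not.

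The logistic covariate is partly a restatement of the outcome, so its coefficient cannot be read as a predictor of success.

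At stake is interpretation. A reader could take an artefact for evidence that re-intervention protects, harms or fails to help. No alpha or study decision rests on these analyses.

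**Working it through.** The plan gives no sample size, power or test level for these sub-analyses, so there is no stated figure to reproduce.

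**Inputs from the document.** De novo dyspareunia 9% (12.1.2.2); follow-up 36 months (8.1); 227 enrolled and 181 evaluable per arm (12.1.1.2).

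**Assumptions.** Weibull hazard from surgery with shape k = 0.3 to 1.5; 10% re-intervened, at random, with no effect on events; intervention time uniform over months 2-12, 6-30 or 18-34. The document gives none of these.

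**1. Cox clock, by hand.** The cumulative hazard is H(t) = -ln(1 - 0.09) x (t/36)^k = 0.0943 x (t/36)^k. Take a woman re-intervened at month 18. The first six months of her clock are months 18-24 after surgery. For comparators with the clock at surgery they are months 0-6. The ratio of accumulated hazard is [(24/36)^k - (18/36)^k] / (6/36)^k:

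- k = 0.5 (falling hazard): (0.8165 - 0.7071)/0.4082 = 0.27
- k = 1 (constant): 0.1667/0.1667 = 1.00
- k = 1.5 (rising): (0.5443 - 0.3536)/0.0680 = 2.80

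The intervention does nothing in any of these cases.

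**2. Cox clock, full model.** The large-sample Cox estimate b solves: sum over clock time u of e1(u) - [e0(u) + e1(u)] x n1(u)exp(b) / [n0(u) + n1(u)exp(b)] = 0. Here n is the proportion at risk and e the expected events, with (1) and without (0) intervention. With the clock at surgery for comparators, exp(b) is:

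| Intervention window | k=0.3 | k=0.5 | k=0.7 | k=1.0 | k=1.5 |
|---|---|---|---|---|---|
| Months 2-12 | 0.43 | 0.63 | 0.80 | 1.00 | 1.25 |
| Months 6-30 | 0.25 | 0.44 | 0.65 | 1.00 | 1.66 |
| Months 18-34 | 0.15 | 0.30 | 0.52 | 1.00 | 2.35 |

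If the comparator's clock starts instead at a visit 0-3 months before surgery, the rows run 0.43 to 1.36, 0.26 to 1.86 and 0.16 to 2.86, and a constant hazard gives 1.06, 1.09 and 1.17. In simulation, a model on time since surgery with a time-dependent intervention indicator gave 0.94 to 1.06 at 10% re-intervened, that is, about 1 within simulation error.

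**3. Expected events.** Over these shapes and windows, the probability of a first event after the intervention is 0.83% to 8.14%. With an assumed 5-15% re-intervened, one arm would have between 227 x 0.05 x 0.0083 = 0.09 and 227 x 0.15 x 0.0814 = 2.77 such events.

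**4. QOL t-test.** Assume no intervention effect, no change between adjacent follow-up visits, equal SDs and a two-sided 5% test. The expected difference is then the index-surgery gain d, in SD units. The noncentrality is d x sqrt(n1 x n2/(n1 + n2)). At 10% of 227, sqrt(23 x 204/227) = 4.55.

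| Assumed gain d | 0.3 | 0.5 | 0.8 | 1.0 |
|---|---|---|---|---|
| Noncentrality | 1.36 | 2.27 | 3.64 | 4.55 |
| Rejection probability | 0.27 | 0.62 | 0.95 | 0.99 |

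Over the same gains the probability is 0.16 to 0.90 at 11 v 216 (5%), 0.36 to above 0.99 at 34 v 193 (15%), and 0.22 to 0.98 at 18 v 163 (10% of 181).

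**5. Covariate overlap.** The composite needs symptomatic success, anatomic success and no retreatment (7.1). A woman coded as having an office intervention for recurrence has, by 11.5, failed the first two at some time, and may have used the pessary named in the third. The overlap is not complete: the endpoint is read at month 36, and an office intervention can also be physical therapy.

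**The case against.** Five counter-arguments deserve an answer.

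**Re-surgery is different.** The Cox figures assume that risk depends only on time since the index operation. A second vaginal operation may restart it. If it does, the planned clock compares risk after the second procedure with risk after the first. In the same settings it gives 1.00 with the clock at surgery and about 1.03 to 1.23 with the baseline lag. A time-dependent model from index surgery then gives 0.42 to 7.4, a valid answer to a different question. The QOL windows allow a similar reading. This stands. A reader might carry the table above over to 12.3.5.3 and 12.3.7, but the documents do not support that, because they do not say which question is meant.

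**Baseline may mean surgery.** Adverse events are recorded only once a woman is enrolled (21.1), and enrolment is at incision (10.1). This stands against the lag figures, including the 2.86 extreme. It does not remove the problem: 0.15 to 2.35 is the range with the clock at surgery.

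**The overlap cannot be sized.** The third component joins surgical retreatment and pessary use with the word or. Read literally, a pessary alone need not mean failure. A reader might derive an odds ratio from an assumed pessary share, but that takes a pessary alone as failure and supposes no other link to the outcome. The recurrence definition in 11.5 contradicts the second supposition. This stands: the overlap is real and its size unknown.

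**Few events.** Large-sample limits say little about a model with 0 to 3 events after intervention, and many such models could not be fitted. Erosion and exposure of a graft also cannot arise in native tissue women without one. This limits the harm but does not correct the contrast, and the QOL test does not depend on event counts.

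**The comparator label is a drafting slip.** Probably so, and easily mended.

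**Conclusion.** The within-arm Cox and QOL comparisons for office-based intervention are wrong as written. The weakness is minor to moderate.

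The fault in the definitions is certain from the text. Its size is not. The document gives no hazard shape, intervention timing, share re-intervened or expected QOL gain, so every figure above is illustrative. A reader might infer that the planned clock always makes intervention look protective. It does so only if the hazard falls after surgery. With the clock at surgery, a constant hazard gives no bias and a rising one makes intervention look harmful. The direction of the QOL artefact is clearer: whenever the index operation improves scores, that gain is credited to the comparators alone.

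For re-surgery the fault is an unstated question, not a demonstrated bias. For 12.3.4, the covariate overlaps the outcome by definition to an unknown degree.

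A reader might also infer that the trial's main conclusions are compromised. They are not. The co-primary tests do not use these analyses. Among re-intervened women, the comparison of Xenform with native tissue starts both arms' clocks at the first intervention, and its QOL comparison uses the same follow-up visit in both arms.

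**What to change.** - **Cox model, office-based intervention (12.3.5.2).** Use time since index surgery for all women, with intervention as a time-dependent covariate (0 before, 1 after), or a landmark analysis. State whether women with an earlier event of the same type stay in the risk set. That choice moves the illustrative hazard ratio by at most about 0.02, but it should be fixed in advance.
- **QOL, office-based intervention (12.3.5.2).** Compare change over the same post-operative visit interval in both groups, or use a repeated-measures model with a time-varying post-intervention indicator. Name one comparator throughout: women without intervention.
- **Re-surgery (12.3.5.3, 12.3.7).** State the question first. If it is the effect of re-surgery against none, use the same time-dependent and matched-interval methods. If it is risk or QOL change after the second procedure against after the first, say so, start both clocks at the respective surgery date and label the result that way.
- **Logistic model (12.3.4).** Drop the intervention covariate, or label the model descriptive. Reconcile the or wording in the third component of the composite (7.1).

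The cost is SAP wording and a little more programming. No new data are needed: interventions and adverse-event onset dates are on the case report forms (11.5, Table 21.6-1), and the QOL instruments are scheduled at months 6, 12, 18, 24 and 36 (Table 11.1-1).

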12.3.5.3. Subjects with surgical intervention for recurrence

The above mentioned analyses for the subgroup with office based intervention for recurrence will be repeated for subjects with surgical intervention for recurrence.

12.3.5.4. Subjects with surgical intervention for recurrence or complications

Each of device-related or procedure-related adverse events during the period after the re-surgery will be summarized by the vaginal compartment(s) (i.e. apical only, anterior only, apical and anterior) treated in the index procedure within each treatment group.

12.3.6. **Additional Data Analyses**

- Assessment of EQ-5D score for health status at 12, 24 and 36 month as compared to baseline
- Assessment of SSQ-8 score for surgical satisfaction at 6, 12, 24 and 36 month

Propensity score adjusted confidence intervals described in Section 12.2.3 (Propensity Score Methodology) will be used to summarize EQ-5D and SSQ-8 score improvements between two groups.

12.3.7. **Sub-Analysis for Interventions for Complications**

The above sub-analyses in Section 12.3.5 (Sub-Analysis for Sling Repair and Interventions for Recurrence) will be repeated for re-surgery for complications or recurrence.

12.3.8. **Interim Analysis**

An interim analysis will be performed at 12 months from the last subject enrolled in the study; all subjects will be followed to 36 months for the primary endpoint and final analysis. This analysis will consist of the primary and some or all of the secondary endpoints and demographics if deemed necessary.

Descriptive statistics by treatment arm along with the 95% confidence interval for the treatment difference will be reported after adjusting for propensity scores¹. The descriptive statistics includes mean, standard deviation, n, minimum, and maximum for continuous variables and frequency statistics for discrete variables.

¹ To support United States Premarket Approval Activities, as agreed to on the Presubmission call held on May 24, 2017 (Q170382), Boston Scientific will submit descriptive statistics for the submission of the PMA, which per reclassification document number 2015-33165, is required to be accepted and filed on or before July 5, 2018.

12.3.8.1. Hypotheses²

The interim analysis hypothesis is that transvaginal biologic mesh repair (treatment) is non-inferior to traditional native tissue repair (control) in both effectiveness and safety at 12 months.

Statistical testing will be performed to evaluate whether transvaginal biologic mesh repair (treatment) is non-inferior to native tissue repair with respect to the composite treatment success endpoint. The null hypothesis is that the success rate for Xenform is inferior to that of the control at a non-inferiority margin of 12%:

$$H_0: \pi_{treatment} - \pi_{control} \leq -12\%$$

where $\pi_{treatment}$ and $\pi_{control}$ is the success rate in the treatment and control group, respectively. The alternative hypothesis is:

$$H_a: \pi_{treatment} - \pi_{control} > -12\%$$

The rejection of null hypothesis indicates the non-inferiority of transvaginal biologic mesh repair.

If non-inferiority is demonstrated, then the superiority of transvaginal biologic mesh repair at 12 months will be evaluated, for which the hypotheses are:

$$H_0: \pi_{treatment} \leq \pi_{control}$$

$$H_a: \pi_{treatment} > \pi_{control}$$

The rejection of null hypothesis indicates the superiority of transvaginal biologic mesh repair.

Statistical testing will be performed to determine if the serious complication rate (i.e. serious adverse device effects and serious procedure-related adverse events) of the treatment group is non-inferior to the control group at 12 months. The null hypothesis is that the serious complication rate in treatment group is greater than or equal to the rate in control group plus margin of 10%:

$$H_0: \pi_{treatment} - \pi_{control} \geq 10\%$$

where $\pi_{treatment}$ and $\pi_{control}$ is the serious complication rate in the treatment group and control group, respectively. The alternative hypothesis is:

$$H_a: \pi_{treatment} - \pi_{control} < 10\%$$

12.3.8.2. Statistical Methods

The comparisons of transvaginal biologic mesh repair to native tissue repair will be based on a two-sided 90% confidence interval for the treatment difference. The confidence interval will be calculated based on the pooling of treatment differences across propensity score strata for a binary endpoint, as described in Section 12.2.3 (Propensity Score Methodology).

² To support the continued review of the Premarket Approval Application for the United States, Boston Scientific will submit hypothesis testing as an Amendment to the initial PMA following acceptance and filing.

Missing 12 month data for the composite efficacy endpoint will be handled by multiple imputation under a logistic regression model using a fully conditional specification. The imputation model will include treatment group and primary efficacy outcome at 2 and 6 month. A total of 5 imputed data sets will be generated.

The following methods will also be used as sensitivity analyses:

- Tipping point analysis
- Observed data only

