7.1. Primary Endpoints

The primary endpoint of the study is to achieve non-inferiority of transvaginal repair with Xenform over native tissue repair at 36 months as compared to baseline.

Success will be based on a composite of objective and subjective measures, and subjects will be considered a surgical success if each of the three criteria is met:

1. Subjective success is achieved if the patient denies symptoms of vaginal bulging per PFDI-20 question 3, answering “no” or “yes” but “Not at all” bothersome (<2).
2. Anatomic success (in the operated compartment):
 - Anterior segment: Leading edge of anterior prolapse is at or above the hymen or POP-Q point Ba \leq 0.
 - Apical segment: The vaginal apex does not descend more than one-half into the vaginal canal (i.e. POP-Q point C < -1/2 TVL) for multi-compartment prolapse or POP-Q point C \leq 0 for single compartment apical prolapse.
3. No retreatment for POP: No additional surgical treatment for POP in the segment(s) of the vagina treated at the index surgery or no pessary use since index surgery (i.e., ‘treated segment’ refers to the target compartments in this study, which are the anterior and apical compartments).

Additionally, a co-primary endpoint of the study is to achieve non-inferiority of transvaginal repair with Xenform to native tissue repair for safety by comparing rates of serious device or serious procedure related complications between baseline and the 36 month time point. Serious injury is defined per 21 CFR 803.3, i.e., life threatening, results in permanent impairment of a body function or permanent damage to a body structure or injury or illness that requires medical or surgical intervention to preclude impairment of a body function or permanent damage to a body structure.

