10.1. Point of Enrollment

Subjects will be considered enrolled in the study once an incision is made in the vaginal wall. All enrolled subjects will have been consented and assigned to receive either the treatment or control procedure per site assignment. Per Boston Scientific's discretion, a site may be considered for participation in both the treatment and control procedure arms however each physician must be designated to one arm only. All enrolled subjects with a surgery initiated (i.e. incision in vagina) will be considered part of the Intent-to-Treat (ITT) population for the final study analysis. All ITT subjects who are treated with a study procedure and had no major protocol deviations will be considered part of the Per Protocol analysis.

The following study timeline (see Table 10.1-1) is based on milestones completed and the current follow-up visit cadence.

Table 10.1-1: Study Timeline

Study Milestones	Dates
Final FDA Approved Protocol	September 2013
First Site Initiated or Enrollment Ready	January 2014
Last Site Initiated or Enrollment Ready	December 2014
First Subject Enrolled	February 2014
Last Subject Enrolled	December 2016
Expected Date of Subject Follow-up Complete	December 2019
Expected Date of Final Database Lock/Study Completion	February 2020
Expected Date of Final Report Submission to FDA	June 2020

All efforts will be made by site staff to ensure minimal loss to follow-up of patients and will follow a site-specific loss to follow-up plan. The plan may include efforts such as telephone

follow-up, Investigator-patient counseling, visit reminder tools, patient stipends if permitted per site IRB, and/or other communication methods.

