12.1.1.3. Statistical Methods

For the primary effectiveness endpoint, non-inferiority will be evaluated using a two-sided 90% confidence interval for the treatment difference (Xenform minus native tissue repair). If the entire confidence interval is above the margin (i.e., -12%), non-inferiority will be demonstrated. The confidence interval will be calculated based on the pooling of treatment differences across propensity score strata for a binary endpoint, as described in Section 12.2.3 (Propensity Score Methodology).

If any data on the primary efficacy endpoint is missing, multiple imputation will be performed in which the missing values will be imputed five times under a logistic distribution model, using a fully conditional specification that includes the treatment arm and the assessments of the treatment success endpoint at each of 2, 6, 12, 18, and 24 months. As

a sensitivity analysis, the comparison of treatments will also be performed using the following methods:

- Tipping point analysis
- Available cases only (i.e., only the subjects for whom the endpoint was assessed)

For the primary safety endpoint, the proportions will be calculated using for the numerator the number of subjects with an endpoint event and for the denominator the number of subjects in the analysis population (ITT and Per Protocol group). Non-inferiority will be evaluated using a two-sided 90% confidence interval for the treatment difference (Xenform minus native tissue repair). If the entire confidence interval is below the margin (i.e., 11.6%), non-inferiority will be demonstrated. The confidence interval will be calculated based on the pooling of treatment differences across propensity score strata for a binary endpoint, as described in Section 12.2.3 (Propensity Score Methodology).

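### The 12-month imputation model in 12.3.8.2 leaves out composite outcomes from Month 18 onward that most women will already have by the interim; adding them would bring a modest gain

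*Combined protocol and SAP*

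**What the plan says.** **Interim model.** Section 12.3.8.2 says that missing 12-month composite data are "handled by multiple imputation under a logistic regression model using a fully conditional specification". On predictors it says "The imputation model will include treatment group and primary efficacy outcome at 2 and 6 month", and on number "A total of 5 imputed data sets will be generated". Tipping point and observed-data analyses are the planned sensitivity analyses.

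**Timing.** Section 12.3.8: "An interim analysis will be performed at 12 months from the last subject enrolled in the study". Table 10.1-1 dates first enrolment to February 2014 and last enrolment to December 2016.

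**Later visits.** Table 11.1-1 schedules POP-Q and PFDI-20 at Months 18, 24 and 36, so the composite continues to be measured after Month 12. Nothing in section 12.3.8 limits the interim data to Month 12 and earlier.

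**Final analysis.** Section 12.1.1.3 uses the same method for Month 36, with treatment arm and "the assessments of the treatment success endpoint at each of 2, 6, 12, 18, and 24 months".

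**The concern.** Follow-up at the interim will run from about 12 to 46 months, so many women will have outcomes recorded after Month 12. For a woman whose Month 12 composite is missing, the Month 18 composite is the nearest later measurement. It can reflect prolapse that returned after Month 6, which the Month 2 and 6 outcomes cannot. Leaving it out makes the analysis rely on a stronger missing-at-random assumption than the data on file require.

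The 12-month comparison feeds a non-inferiority test and then, if that succeeds, a superiority test. Both are intended for the premarket application (section 12.3.8.1 and its footnote). If women whose repair fails between Months 6 and 12 miss that visit more often in one arm, the imputed difference is biased, and part of that bias could be removed with data already collected.

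**Working it through.** **1. The plan's own figures.** With 70% success in both arms, a 12-point margin, one-sided alpha 0.05 and 80% power (12.1.1.2): n = (1.645 + 0.842)² × 2 × 0.70 × 0.30 / 0.12² = 180.3, so 181 per arm. Then 181 / 0.80 = 226.25, so 227 per arm and 454 in all. Both match the plan. No stated number is in dispute.

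**2. Who has passed each visit at the interim.** Accrual spans 34 months (February 2014 to December 2016), and the interim falls at month 46. The share past Month m is F((46 − m)/34), where F is the accrual curve. The documents do not give F, so several are tried, with u = (46 − m)/34.

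| Assumed accrual | Past Month 18 | Past Month 24 | Past Month 36 |
|---|---|---|---|
| Early-weighted, √u | 91% | 80% | 54% |
| Uniform, u (28/34, 22/34, 10/34) | 82% | 65% | 29% |
| Uniform from December 2014 (18/24, 12/24) | 75% | 50% | – |
| Late-weighted, u² | 68% | 42% | 9% |
| Strongly late-weighted, u³ | 56% | 27% | 3% |

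A majority has passed Month 18 in every row. That is not so for Month 24.

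**3. Whether the relevant missing pattern can occur.**
- Section 11.4.5 counts Month 12 as missed only when the Month 18 window opens. A woman with a missed Month 12 who is still in the study has therefore reached that window.
- Section 10.2.3 requires two consecutive missed visits before loss to follow-up, so a missed Month 12 can be followed by an attended Month 18.
- The phone visit in section 11.4.5 covers adverse events, risk factors, analgesics and mailed questionnaires. It includes no POP-Q, so the composite is incomplete.

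The documents do not say how many women will show this pattern.

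**4. Size under differential missingness (all inputs assumed).** Month 6 success is 85%. Month 12 success is 90% after Month 6 success and 25% otherwise. Later-visit success is 94% after Month 12 success and 20% otherwise. In the Xenform arm, Month 12 failures are missing at 30% and successes at 12%. In the control arm 15% are missing regardless of outcome, so it contributes no error.

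Per 100 Xenform women, let a cell hold S true successes and F true failures at Month 12. Missing women number 0.12S + 0.30F. They are imputed at the rate seen in attenders, r = 0.88S/(0.88S + 0.70F). The error is (0.12S + 0.30F)r − 0.12S. Month 2 and imputation noise are left out.

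| Predictors | Cell | S | F | r | Error |
|---|---|---|---|---|---|
| Month 6 | success | 76.5 | 8.5 | 0.919 | 1.597 |
| Month 6 | failure | 3.75 | 11.25 | 0.295 | 0.680 |
| Month 6 + later | success, success | 71.91 | 1.70 | 0.982 | 0.341 |
| Month 6 + later | success, failure | 4.59 | 6.80 | 0.459 | 0.638 |
| Month 6 + later | failure, success | 3.525 | 2.25 | 0.663 | 0.305 |
| Month 6 + later | failure, failure | 0.225 | 9.00 | 0.030 | 0.056 |

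Month 6 alone favours Xenform by 1.597 + 0.680 = 2.28 points. If every missing woman were seen later, 1.34 points would remain. If a share q is seen later, the bias is 2.28 − q(2.28 − 1.34):
- q = 0.3: 2.00 points, a reduction of 0.28 (12%)
- q = 0.5: 1.81 points, a reduction of 0.47 (21%)
- q = 0.7: 1.62 points, a reduction of 0.66 (29%)

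Simulation of the same scenario with 227 per arm agrees: 2.2 to 2.4 points falling to 1.5 to 2.1.

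**5. A more favourable mechanism.** A second simulation used N = 454, correlated binary outcomes, Months 2 and 6 with five imputations, and 250 trials per setting. Missingness in the Xenform arm depended on the Month 18 outcome itself. The shift from complete data was 0.8 to 2.2 points without Month 18 and 0.5 to 1.6 with it. The gain ranged from 0.81 − 0.58 = 0.23 to 2.13 − 1.13 = 1.00 points. This is the mechanism that suits adding Month 18 best, so it is an upper guide.

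**6. Ignorable missingness.** Neither model is biased. The standard error falls by about 1% to 2% at most, and a single trial's estimate moves with a standard deviation of 0.5 to 0.7 points.

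**The case against.** The strongest reply is that the harmful scenario is missing-not-at-random, for which the plan already specifies a tipping point analysis. Adding later visits leaves most of the bias in place: 1.62 to 2.00 of 2.28 points in step 4. That stands, and the tipping point analysis remains the main check. But it explores what is unknown; it does not use outcomes already on file.

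The effect is also small beside a 12-point margin and a standard error near 4 points. In simulated trials of the step 4 scenario with no true difference, the non-inferiority verdict changed in only 0.4% to 0.8%. The missingness inputs come from outside the documents. Women who left before Month 12, and the last enrolees, have no later data. All of this stands.

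A reader might infer three stronger points that the documents do not support:
- **That the interim model contradicts the Month 36 model.** It does not. Each uses only visits before its own endpoint, which is a consistent and defensible convention.
- **That success at Month 18 proves there was no retreatment by Month 12.** Criterion 3 in section 7.1 joins further surgery and "no pessary use since index surgery" with the word or. The inference needs the reading that neither occurred, and it covers only one of three components. A Month 18 failure may also have arisen after Month 12.
- **That most women will have passed Month 24.** This depends on the accrual curve.

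**Conclusion.** The point holds as a modest improvement to the analysis; no error or contradiction in the plan is shown. The listed predictors stop at Month 6, while the plan's own dates put most women past Month 18 at the interim under every accrual curve tried (56% to 91%). For those who lack a Month 12 composite but return later, useful outcomes go unused.

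Under the assumed inputs, using them would remove roughly 10% to 30% of any bias from differential missingness, about 0.2 to 0.7 points, and change the standard error by at most 1% to 2%. A reader might infer that the 12-month conclusion is unsafe as planned, or that later visits would make it safe. Neither is shown: no verdict is shown to change, and most of any such bias would remain. The size rests on the assumed outcome and missingness rates and on the unknown number of women with this missing pattern.

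**What to change.** In section 12.3.8.2, add the composite at Month 18 as an auxiliary predictor in the fully conditional specification, using visits observed at a stated interim data cut. Add Months 24 and 36 where enough women have them, and say in advance what counts as enough. Keep Month 12 as the analysed endpoint, and keep the tipping point and observed-data analyses.

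No new data are needed. The cost is a slightly larger imputation model in which some visits have not been reached: under uniform accrual, 18% of women are short of Month 18, 35% of Month 24 and 71% of Month 36. The model should be checked for stable fits with those gaps. The text sits in the protocol, so the change needs the approvals in section 14, and it should be made before the interim outcomes are analysed.
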